## **9. Statistical Analysis**

The statistical test methods are described in the statistical analysis plan.

## **10. Data management**

The investigator is responsible for the correct and complete entry of patient data into the case report form (CRF). A patient number (see 6.2.) is assigned to each patient on the CFR. The CRF is kept for 15 years. Any publication of data is anonymous.

The patient will be informed by the investigator about the valid privacy policy. The patient will receive a copy of the privacy policy signed by the patient with place and date. The original is deposited in the study file.

## **11. Ethical, legal and administrative aspects**

The investigator ensures that the test is performed in accordance with existing laws and regulations (ICH and GCP Guidelines, AMG). The study protocol and patient information are submitted to the Ethics Committee of the University of Rostock.

Before starting the study, each patient must give written consent to the investigator, having previously been fully informed in an understandable manner about the nature, significance and scope of the clinical trial. The content of this information is documented on the consent form. The patient will be given a copy of the signed consent form. The original is deposited in the study file.

## **12. Publication**

The aim is to publish the results of the study in a scientific journal.

## **13. Sponsorship and conflict of interest**

The investigators declare no conflicts of interest.

## **14. Amendments**

Any change to the study protocol will be substantiated and documented. The changes are considered part of the study protocol.

## **17. Attachements**

Attachement 1      Informed Consent Form  
Attachement 2      Case Report Form

### **Final Version**

**Date 29.06.2019**

## **Statistical Analysis Plan**

The metric parameters are described by mean value (Mw) and standard deviation (Sd). The Mann-Whitney U test tests whether the two groups differ in the distribution of the parameter. If the p-value of the test is less than the selected significance level (0.05), then the groups differ significantly in terms of distribution.

Categorical parameters (0/1) are described by the exact Fisher test. The exact Fisher test examines whether each parameter is independent of its membership in a group. If the p-value of the test is less than the selected significance level (0.05), then there is a significant dependence. The two groups then differ significantly with respect to the selected parameter.

The incidence of adverse events in the two groups is described with odds ratios (95% confidence interval).

Statistical analyses were performed bilaterally, using GraphPad PRISM 8.0 (GraphPad Software Inc., San Diego, CA, USA).

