## Patient population

Adult men and women undergoing surgical treatment of proximal femoral fractures.

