## **2. Primary and secondary outcome parameters**

With the present prospective study design, we examine whether the surgical treatment of proximal femoral fractures exclusively under peripheral regional anaesthesia (blockade of the lumbosacral plexus) is a reliable anesthesia procedure. The main objective is to determine the frequency of necessary supplementation by analgesics/sedatives (criterion 1) or the conversion rate (criterion 2) to general anaesthesia (infra- or supraglottic airway). Side effects (e.g. delirium and pneumonia rates), hospital length of stay and hospital mortality are recorded.

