## **3. Study design**

This is a single-center prospective study.

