### **6.2. Allocation of the study medication**

After admission to the study, each patient receives a patient number, which is noted on the Case Report Form (CRF).

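### The SAP plans only comparisons between two groups that neither document defines, and plans no confidence interval for the supplementation and conversion proportions that are the main objective

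*SAP*

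**What the plan says.** Section 2 of the protocol sets the aim: "The main objective is to determine the frequency of necessary supplementation by analgesics/sedatives (criterion 1) or the conversion rate (criterion 2", the latter meaning conversion to general anaesthesia. Section 9 consists of one sentence: "The statistical test methods are described in the statistical analysis plan".

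The SAP gives mean and standard deviation for metric parameters and then states: "The Mann-Whitney U test tests whether the two groups differ in the distribution of the parameter". For binary data, "Categorical parameters (0/1) are described by the exact Fisher test". For safety, "The incidence of adverse events in the two groups is described with odds ratios (95% confidence interval". The significance level is 0.05 and the tests are two-sided. The SAP mentions neither criterion 1 nor criterion 2, and it defines no analysis set.

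On design, section 3 says "This is a single-center prospective study". The synopsis gives one population: "Adult men and women undergoing surgical treatment of proximal femoral fractures". Section 6.2 has allocation in its title but assigns only an identifier: "After admission to the study, each patient receives a patient number, which is noted on the Case Report Form (CRF". Section 6.4 describes one technique with three injection targets. Section 8 keeps supplemented and converted patients in the study. It also lists drop-outs caused by the intervention, without saying whether they stay in the denominator.

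**The concern.** The objective asks for the size of two proportions among patients who receive the block. Apart from mean and standard deviation, the SAP answers a different question: whether two groups differ. A test yields a p-value, not a rate, so assigning the description of 0/1 parameters to Fisher's test leaves the estimate that the trial needs outside the plan.

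Two things are at stake. First, section 2 asks whether the block is a reliable method of anaesthesia, and the answer could be published as a bare percentage. Second, p-values at 0.05 and odds ratios are prescribed for a comparison whose groups would have to be chosen after the data are seen.

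**Working it through.** The plan contains no sample size, expected rate or precision target, so there is no figure to reproduce. The check has three parts.

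**1. Who could the two groups be?** The documents select none of these readings.

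| Reading | What the documents offer | Consequence for the SAP |
|---|---|---|
| Single cohort, no split | Synopsis, sections 3, 6.2 and 6.4 | There is no second group, so none of the tests or odds ratios can be computed |
| Split by supplementation | Intervention D in the synopsis is supplemental medication | The groups are formed by criterion 1, so testing criterion 1 between them is circular |
| Outside comparator under spinal or general anaesthesia | The introduction postulates fewer side effects | No source, eligibility or data collection is given, and conversion to general anaesthesia has no obvious counterpart in patients already under it |

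The circularity can be shown with an assumed 20 supplemented patients among 100. The table of group by criterion 1 is then [20, 0; 0, 80], and Fisher's p = 1 / C(100, 20) ≈ 2 × 10⁻²¹. That value follows from the construction and says nothing about the block.

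**2. What would the missing interval show?** For x events in N patients, the exact (Clopper-Pearson) 95% limits are

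- lower = 2.5% quantile of Beta(x, N − x + 1)
- upper = 97.5% quantile of Beta(x + 1, N − x)

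With x = 0 the upper limit is 1 − 0.025^(1/N); for N = 50 this is 1 − 0.025^0.02 = 7.1%. All values of N and all rates here are assumptions.

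| N | Assumed 10% | Assumed 20% | Upper limit with zero events |
|---|---|---|---|
| 50 | 3.3–21.8% | 10.0–33.7% | 7.1% |
| 100 | 4.9–17.6% | 12.7–29.2% | 3.6% |
| 200 | 6.2–15.0% | 14.7–26.2% | 1.8% |

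At 20% the widths are 23.7, 16.5 and 11.5 percentage points. Wilson limits are close (20/100: 13.3–28.9%), so the choice between the two methods is minor.

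**3. How much does the drop-out rule matter?** Assume 50 patients, 5 conversions, and 3 other patients who drop out because of the intervention.

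- Kept in N, not counted as events: 5/50 = 10.0% (3.3–21.8%)
- Removed from N: 5/47 = 10.6% (3.5–23.1%)
- Kept in N and counted as failures: 8/50 = 16.0% (7.2–29.1%)

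Removing them changes little. Whether they count as failures changes more.

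**The case against.** The strongest reply is that a frequency and a rate are already simple proportions, that section 9 sends only the test methods to the SAP, and that nothing there forbids reporting n/N with an interval. On this view the SAP is thin but does not block the objective. Section 8 also settles part of the denominator by keeping supplemented and converted patients. These points stand, and it would be wrong to say that the plan has no estimand or no denominator at all. They do not supply the interval, the drop-out rule or the identity of the two groups.

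A reader might also infer more than the documents support:

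- **That sufentanil given before the block makes criterion 1 100%.** Section 6.3 places that dose in preoperative preparation, before there is a block to supplement, and section 2 speaks of necessary supplementation.
- **That the main outcome is an ambiguous composite.** The two criteria are numbered separately and read naturally as two proportions.
- **That the drop-out rule could remove conversions**, for example turning 5/100 into 3/98. Section 8 says that converted patients are not excluded. If two drop-outs who were not converted are removed, 5/100 = 5.0% (1.6–11.3%) becomes 5/98 = 5.1% (1.7–11.5%), which is almost unchanged.

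Finally, some front and administrative pages of both documents and the case report form were not available for this review and could bear on definitions. The SAP's methods text and the protocol's design, population, allocation and intervention sections were available, and none of them defines groups.

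**Conclusion.** The point holds: the SAP's inferential methods do not fit the main objective. Every test and odds ratio needs two groups that are not identified in the available text, and the only planned interval is for adverse-event odds ratios. This is an error in the plan as written, and more than missing detail, because following the SAP gives no interval for either main proportion.

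That the study has a single arm is inferred; the protocol never uses the term. The conclusion does not depend on it, since an internal split and an outside comparator are equally unspecified. The size of the problem can only be illustrated: at an assumed 20% rate the unreported uncertainty spans 23.7 percentage points with 50 patients and 11.5 with 200. The treatment of drop-outs caused by the intervention is a smaller open point, and its direction and size depend on assumptions.

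**What to change.** In the SAP, before the data are analysed:

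1. Make the primary analysis n/N with an exact (or Wilson) two-sided 95% confidence interval, separately for criterion 1 and criterion 2. Use as denominator all patients in whom the block was started, keep drop-outs caused by the intervention in N, and state how they are counted.
2. Report delirium, pneumonia, other side effects and hospital mortality as proportions with 95% confidence intervals.
3. Either name the two groups and their source in advance, label the comparison exploratory and do not test the outcome that defines the groups, or delete the two-group tests and odds ratios.

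If the comparisons are deleted or an internal split is named, the cost is a short SAP rewrite with no extra patients or procedures. If an outside comparator was intended, its source, eligibility and data collection must be defined, probably by protocol amendment. The downsides are that intervals may be wide at small N and that this cohort alone can support no claim of fewer side effects than under spinal or general anaesthesia.

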### Study design

single-center, prospective

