## Interventions

Intervention A	20ml ropivacaine 0.375% (parasacral sciatic nerve block)
Intervention B	20ml ropivacaine 0.375% (psoas-compartment block)
Intervention C	20ml ropivacaine 0.375% (transmuscular quadratus-lumborum block)
Intervention D	Supplemental analgesic (sufentanil) and/or sedative (propofol) medication

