#### **6.4. Interventions**

The ultrasound-guided regional anesthesia is performed by two experienced anesthetists. We use a Sonosite (EDGE) ultrasound device with convex transducer (C60 2-5MHz) and a Pajunk 21G-100mm Sonoplex needle in in-plane technique. At the same time, the needle position is confirmed by nerve stimulation (dual guidance concept). For this purpose we use a Stimuplex HNS12 from Braun, Melsungen, Germany (frequency 2Hz, pulse width 0.1ms, stimulation limit <1mA).

Double injection technique with three (1a-c) target structures. (Resulting Anaesthesia level Th12-S3)

Intervention 1a      20ml Ropivacaine 0.375%. Parasacral ischiadicus block (18)  
Segments L4-S3

Intervention 1b      20ml Ropivacaine 0.375% Psoas compartment block (16)  
Segments L2-L4

Intervention 1c      20ml Ropivacaine 0.375% transmuscular quadratus-lumborum block (20) Segments T12-L1

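### The SAP's tests and odds ratios all compare two undefined groups, while the protocol describes one regimen and the main objective has no planned estimate or interval

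*SAP*

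**What the plan says.** The SAP is one short section. Metric parameters get a mean and standard deviation and a Mann-Whitney U test between two groups. For 0/1 parameters the only stated method is Fisher's test: "The exact Fisher test examines whether each parameter is independent of its membership in a group". A p-value below 0.05 leads to the conclusion "The two groups then differ significantly with respect to the selected parameter". For adverse events, "The incidence of adverse events in the two groups is described with odds ratios (95% confidence interval". Testing is two-sided. No adjustment, stratification or matching is named.

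The protocol states the design in section 3: "This is a single-center prospective study". Section 6.4 describes one technique: "Double injection technique with three (1a-c) target structures". The synopsis lists the same three injections as A to C, plus supplementary medication as D. Section 6.2, whose title refers to allocation, says only: "After admission to the study, each patient receives a patient number, which is noted on the Case Report Form (CRF".

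Section 2 makes the main objective the frequency of supplementation (criterion 1) or the rate of conversion to general anaesthesia (criterion 2). It says that side effects, length of stay and hospital mortality are recorded. Under section 8, patients who are supplemented or converted remain in the study. Section 9 defers all statistical methods to the SAP. The Introduction postulates that side effects such as delirium and circulatory instability, which it links to spinal and general anaesthesia, are less frequent under peripheral block.

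**The concern.** A two-group test needs two groups, and the visible text supplies one treated cohort. Two things follow.

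The question that the protocol puts first, how often the block alone is not enough, calls for a proportion and an interval in the treated patients. The SAP plans neither.

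For the remaining outcomes, the meaning of each p-value and odds ratio depends on a definition that is not given. If the groups are chosen after the data are seen, the question is chosen then too. If they turn out to be block versus other anaesthesia, the results would naturally be set against the postulate, although differences in who received which procedure could produce or hide a difference.

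**Working it through.** **Step 1. Look for the two groups in the protocol.**

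| Candidate | What the protocol says | Does it define two groups? |
|---|---|---|
| Interventions A to C (synopsis; 1a to 1c in 6.4) | Three target structures of one technique | No, they are components |
| Intervention D (synopsis; section 8) | Supplementary medication, given if necessary | Not as an allocated arm |
| Section 6.2 | A patient number | No |
| Synopsis and section 3, design | Single-centre, prospective | No comparator or randomisation |
| Section 9 | Refers to the SAP | No |

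**Step 2. Apply the SAP to the main objective.** Supplementation and conversion are yes/no outcomes. The SAP's only stated method for such outcomes is the two-group Fisher test. With one cohort the test cannot be run, and no proportion or interval is specified in its place. If the groups were supplemented or converted versus not, the main outcome would itself define the groups and could not be tested between them.

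**Step 3. Go through the possible definitions for the other outcomes.**

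1. Block versus spinal or general anaesthesia: non-randomised and unadjusted, so any procedure effect is mixed with case mix. Sections 5.1 and 5.2 list no restriction by ASA class. Section 6.7 expects benefit especially in high-risk patients, so selection by risk is plausible, but its direction is unknown.
2. Supplemented or converted versus not: groups formed after treatment starts, with no spinal or primary general-anaesthesia comparator, so the postulate is not tested.
3. A baseline feature such as ASA class or age: acceptable as description; the postulate is again not tested.

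**Step 4. Illustrate the size under definition 1 only.** The plan gives no figure to reproduce: the visible text has no sample size, power or event rate by group. The only usable gradient is for hospital mortality, 5 to 20% in ASA 3-4 (Introduction). Assumed, not in the documents: mortality 12.5% in ASA 3-4 (middle of that range) and 1% in ASA 1-2; the share *s* of ASA 3-4 in each group; 50, 100 or 200 patients per group.

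Group risk = *s* × 0.125 + (1 − *s*) × 0.01. Crude OR = odds in the block group / odds in the other group. Rejection is the exact probability of a two-sided Fisher p < 0.05.

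For 70% versus 50% ASA 3-4 and no true effect: 0.7 × 0.125 + 0.3 × 0.01 = 0.0905; 0.5 × 0.125 + 0.5 × 0.01 = 0.0675; OR = (0.0905/0.9095)/(0.0675/0.9325) = 1.37.

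| ASA 3-4 share, block v other | Risks | Crude OR | Rejection at 50/100/200 per group |
|---|---|---|---|
| 60% v 60% | 0.0790 v 0.0790 | 1.00 | 1.45/2.72/3.21% |
| 70% v 50% | 0.0905 v 0.0675 | 1.37 | 2.34/5.56/9.89% |
| 80% v 40% | 0.1020 v 0.0560 | 1.91 | 5.45/15.60/33.24% |

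With ASA 3-4 mortality at 5% and 20% instead of 12.5%, the ORs run from 1.28 to 1.42 (70 v 50) and from 1.64 to 2.05 (80 v 40).

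Masking: assume a true OR of 0.5 within each class and the sicker patients in the block group. The class risks become 0.0667 and 0.0050. The crude OR is then 0.70 (0.0482 v 0.0675) for 70 v 50 and 0.97 (0.0543 v 0.0560) for 80 v 40. Even with equal mix, Fisher's test detects this effect in only 3.61/12.22/27.04% of studies.

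**Step 5. Deaths available for adjustment at 100 per group.** No effect: 100 × (0.0905 + 0.0675) = 15.8. True OR 0.5: 100 × (0.0482 + 0.0675) = 11.6 for 70 v 50, and 100 × (0.0543 + 0.0560) = 11.0 for 80 v 40. These counts apply to mortality alone.

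**The case against.** The best reply is that confounding criticises a use that the documents do not plan. No spinal or general-anaesthesia cohort is named, section 2 has side effects recorded rather than compared, the postulate is introductory text, and the SAP's wording is about association. This largely stands. A reader might infer that the study is a confounded comparison of block with conventional anaesthesia; the documents do not establish that, so the confounding point stays conditional. Nor is there an error in the tests themselves, and a crude contrast may still be reported as description.

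The illustration is also limited. It concerns mortality, whereas the postulate concerns side effects such as delirium and circulatory instability, for which the documents give no ASA gradient. Its case mixes, group sizes and low-risk mortality are assumed. With 70% versus 50% it adds little: 2.34% rejection at 50 per group and 5.56% at 100. Power for mortality is low even with equal mix. It shows that distortion is possible, not that it is likely.

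Pages were removed from both documents and the case report form is not available, so a group label there cannot be excluded. The statement is therefore about the visible text. The mismatch itself rests on text that is present: one regimen, a patient number as the only allocation, and two-group procedures.

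A reader might also infer that the main objective is untouched because it needs no second group. The SAP does not support that comfort, since its only method for yes/no outcomes is the two-group test.

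**Conclusion.** The point holds as a mismatch between the analysis rules and the design described in the visible text. The main objective lacks a planned estimate and interval, and the comparisons of side effects, length of stay and mortality have no identifiable question. Neither conclusion depends on the assumed numbers.

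The further consequence is conditional. If the groups are block versus spinal or general anaesthesia, the planned contrast could not support a causal reading of the postulate. In the mortality illustration, case mix alone moves the odds ratio from 1 to between 1.28 and 2.05, depending on the imbalance and on ASA 3-4 mortality between 5 and 20%. The distortion can be small, and its direction is unknown. The change should be made. It is cheap and, apart from data for any comparator, a matter of SAP wording.

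**What to change.** 1. In all cases, make the supplementation and conversion proportions, with exact 95% confidence intervals, the main analysis.
2. If there is no comparator, say that the study is non-comparative, delete the between-group significance rule and the odds ratios, and report side-effect proportions with 95% confidence intervals.
3. If a comparator is intended, name it, its source and its period, and state in which group converted patients are counted. Replace the crude odds ratios, and the Mann-Whitney test for length of stay, with estimates adjusted for a short pre-specified set of baseline factors recorded in both groups, for example ASA class and age. Set the number of factors separately for each outcome from its expected events. Label the results exploratory associations.
4. If the groups are formed by a baseline feature, or by supplementation or conversion, label the contrast descriptive and do not use it to support the postulate.

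Items 1, 2 and 4 cost only SAP wording. Item 3 needs a check that the baseline data exist for the comparator: the visible protocol provides for recording co-morbidities and co-medication (sections 5.3 and 5.4) but says nothing about an outside group. The price is weaker claims and, under item 3, wider intervals.

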### Introduction

Older multimorbid patients with hip fractures are a growing patient population due to demographic developments in western industrial nations. Hospital mortality increases with anesthesia risk and ranges from less than 1% (ASA (American Society of Anesthesiologists) Physical Status 1) to 50% (ASA PP 5). This presents the team with a number of challenges when patients are at high risk of anesthesia (ASA PP 3-4, associated hospital mortality 5-20%).

Surgical treatment can be performed under general or spinal anesthesia. Additional peripheral nerve blocks contribute to perioperative pain therapy.

The aim of the study is to demonstrate that the surgical treatment of proximal femoral fractures is possible using a peripheral regional anesthesia procedure.

Both spinal and general anesthesia can contribute to side effects such as postoperative delirium or circulatory instability. We postulate that these side effects occur less frequently when the procedure is performed under peripheral regional anesthesia.

We perform a double injection technique (dual-guidance concept: ultrasound and nerve stimulation). The first injection targets the sacral plexus under the piriformis muscle.

A second injection targets the lumbar plexus: psoas-compartment-block (segments L2-L4) and transmuscular quadratus-lumborum block (segments Th12-L1).

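### The SAP summarises adverse events by odds ratios and other 0/1 outcomes by Fisher's test, so the plan yields no rate with a confidence interval for the frequencies the protocol sets out to determine

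*SAP*

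**What the plan says.** The SAP, which is a single short section, says of adverse events: "The incidence of adverse events in the two groups is described with odds ratios (95% confidence interval". For binary outcomes generally it says: "Categorical parameters (0/1) are described by the exact Fisher test", with the reading rule "If the p-value of the test is less than the selected significance level (0.05), then there is a significant dependence". Testing is two-sided: "Statistical analyses were performed bilaterally, using GraphPad PRISM 8.0". Metric parameters get a genuine descriptive summary (mean and standard deviation). Binary parameters get none: counts, percentages and per-group intervals are not mentioned.

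Protocol section 2 sets out what the study is to find: "The main objective is to determine the frequency of necessary supplementation by analgesics/sedatives (criterion 1) or the conversion rate (criterion 2". It continues: "Side effects (e.g. delirium and pneumonia rates), hospital length of stay and hospital mortality are recorded". Protocol section 9 leaves the statistical methods entirely to the SAP, so nothing in the protocol fills the gap.

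On design, protocol section 3 says only "This is a single-center prospective study". Section 6.4 describes one set of blocks. Neither document defines the two groups to which the SAP refers.

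**The concern.** The study's questions are about how often things happen: how often the blocks need supplementing, how often the anaesthetic is converted, and how often delirium or pneumonia follows. Each answer is a proportion with an interval. An odds ratio compares two groups and carries no information about the level of risk in either; a Fisher p-value carries less still. Supplementation and conversion are themselves 0/1 outcomes, so the gap reaches the main objective as well as the adverse events.

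At stake is whether the report can answer its own main question in a way fixed in advance. The protocol's study goal expects the results to improve patient safety, and judging that needs absolute risks. Because the SAP also leaves the interval method open, that choice could be made after the data are seen.

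**Working it through.** Neither document states a sample size, an event count or an adverse-event rate for the study, so there is no planned figure to reproduce. All group sizes, risks and counts below are assumptions for illustration. The one event rate in the documents that gives a usable range is background: "ASA PP 3-4, associated hospital mortality 5-20"% in the protocol's introduction.

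**1. An odds ratio does not determine an incidence.** Fix OR = 0.5 and vary the risk p0 in one group. The odds in the other group are 0.5 × p0/(1 − p0), and its risk is odds/(1 + odds).

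| p0 | odds in other group | risk in other group |
|---|---|---|
| 1% | 0.00505 | 0.50% |
| 5% | 0.0263 | 2.56% |
| 20% | 0.125 | 11.1% |
| 50% | 0.5 | 33.3% |

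One reported value fits all four rows, whose absolute differences run from about 0.5 to 16.7 percentage points.

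**2. Odds ratio against risk ratio.** OR = [p1/(1 − p1)]/[p0/(1 − p0)]. For a true risk ratio of 2:
- p0 = 1%: OR 2.02
- p0 = 5%: OR 2.11
- p0 = 10%: OR 2.25
- p0 = 20%: OR 2.67

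For a true risk ratio of 0.5 the values are 0.497, 0.487, 0.474 and 0.444. Across the 5–20% range, taken as p0, a risk ratio of 2 therefore appears as an odds ratio of 2.11 to 2.67. The gap matters only to a reader who takes the odds ratio for a risk ratio, and it is small when risks are low.

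**3. Zero cells.** If each group has n patients and risk p, a given group has no events with probability q = (1 − p)^n. At least one group is empty with probability 1 − (1 − q)², and both are empty with probability q². With n = 50:

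| p | q | at least one empty | both empty |
|---|---|---|---|
| 1% | 0.605 | 84% | 36.6% |
| 2% | 0.364 | 60% | 13.3% |
| 3% | 0.218 | 39% | 4.8% |
| 5% | 0.077 | 15% | 0.6% |

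The Wald interval on the log odds ratio needs the reciprocal of every cell, so it fails in the third column's cases. The odds ratio itself is undefined (0/0) only in the fourth column's cases; with one empty group it is 0 or infinite.

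**4. Why the interval method needs naming.** Take 0/50 against 5/50. The sample odds ratio is 0. The conditional exact 95% interval is 0 to 1.05 (Fisher p = 0.056). Adding 0.5 to each cell gives 0.082, with interval 0.004 to 1.52. Both are available under the SAP as worded, and they differ.

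**5. What per-group reporting gives on the same data.**
- 0/50 is 0%, with exact upper limit 1 − 0.025^(1/50) = 7.1%.
- 5/50 is 10%, with exact interval 3.3% to 21.8% (beta quantiles with parameters 5, 46 and 6, 45).
- The risk difference is 0 − 10 = −10 points.

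The per-group lines need no comparison group, so they also work for one cohort. An odds ratio does not.

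**The case against.** The strongest reply is that this is only a matter of reporting. Fisher's test needs the 2×2 counts, so numerators and denominators will exist. Section 2 of the protocol speaks of rates, so rates are plainly intended. The SAP does promise a 95% interval, on the odds ratio. All of that is true. But a SAP marked as final is read for what it commits to, and it does not commit to a proportion or an interval on one, even for the main objective.

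Three stronger readings are tempting and should not be drawn.

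- **That odds ratios overstate the effect.** An odds ratio is valid on its own scale, and the SAP does not call it a risk ratio. It misleads only if read as one, and the gap is small up to risks of about 10%.
- **That the method breaks down whenever a group has no events.** Only the Wald interval does, and the SAP does not commit to it. With one empty group an exact interval exists and is informative.
- **That delirium is known to be common, and pneumonia, toxicity or death rare, in this study.** The documents give no rates for the first three. For death, the background figure of 5–20% in ASA 3–4 patients argues against calling it rare in that group.

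It is also fair to say that the undefined groups are the more basic problem in the same sentence: until they are defined, no between-group measure can be computed, including a risk difference. That stands, and it is a further reason to put per-group proportions first. The choice of a risk difference over a risk ratio is partly preference.

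**Conclusion.** The point holds as a mismatch between the stated objectives and the planned summaries. The protocol asks for frequencies; the SAP provides an odds ratio and a p-value, and neither contains one. Followed literally, the analysis gives no rate with an interval for supplementation, conversion, delirium, pneumonia or hospital mortality, and no odds ratio at all if the study is the single cohort described. This rests on the wording of the two documents and needs no assumed numbers.

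The missing interval method and zero-cell rule are a secondary matter. Their practical weight depends on assumed inputs: with 50 per group, the chance of at least one empty group runs from 15% at 5% risk to 84% at 1%, and the chance of an undefined odds ratio from 0.6% to 36.6%. The documents fix neither the group size nor the risks. The change should be made, but this is a gap in specification that wording can close. It does not make the data uninterpretable.

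**What to change.** Replace the SAP's adverse-event sentence with wording such as:

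> For each 0/1 outcome, including supplementation, conversion and each adverse event, we report n/N, the percentage and the exact (Clopper-Pearson) 95% CI per group. If two defined groups are compared, we also report the risk difference with a Newcombe 95% CI beside the Fisher p-value; any odds ratio is supplementary, with an exact 95% CI whether or not a cell is zero.

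The odds ratio should not be dropped when a cell is zero: that would make reporting depend on the data and remove it where the contrast may be largest. The SAP must separately define the two groups, or state that there is one; the first sentence of the replacement works either way.

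The cost is SAP wording and slightly longer tables, with no new data. For common events, effects may look smaller than they would as odds ratios. A Newcombe interval and a Fisher p-value can also disagree near the 5% level. For 0/50 against 5/50 the Wilson limits are 0 to 7.13% and 4.35% to 21.36%. The Newcombe limits for the difference are then −10 − (21.36 − 10) = −21.4 points and −10 + √(7.13² + (10 − 4.35)²) = −0.9 points. That excludes zero although p = 0.056, so the SAP should say in advance that the interval describes and the test decides.
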